### 5A2.4 \* If "B", please describe how individuals will be selected into the intervention/treatment and control groups (e.g., random assignment of individuals/groups or quasi-experimental designs comparing existing groups). If already described above in 5A1, please indicate that below.

A blocked 1:1 randomization design with stratification by viral suppression (with randomly alternating blocks of 2, 4, and 6 to prevent anticipation of condition) will help to ensure balance across arms. The statistician will use a random numbers generator to devise a randomization log and a set of numbered randomization envelopes. In the log, treatment assignment specifications will be left blank to prevent condition foreknowledge. After the project director records each ID in the log (immediately after the baseline survey, using results from pre-baseline confirmation of viral load via medical records for stratification), s/he will open the corresponding randomization envelope.

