## 5D Procedures - Secondary Data

---

5D1 \* Which previously collected person-level information (e.g., medical records, census data, employment records, education records, other existing datasets) will you acquire? If unsure, please list what you are considering.

Participants will provide consent for paper and electronic medical record data extraction from their usual HIV clinic. During screening, we will obtain permission to extract the two most recent viral loads from medical records, for use in stratification by viral suppression for the randomization process. After the 12-month follow-up, we will extract past 2-year viral load, CD4 counts, ART prescriptions, clinic visits, and associated dates. We have successfully used multiple methods to obtain such data from multiple different clinics across Los Angeles County (e.g., confidential faxes, multiple calls, in-person clinic visits, asking participants to bring lab print-outs to study visits) in prior studies.

At study enrollment and 6- and 12-months post-enrollment (and post-intervention start), a member of the study team (trained in phlebotomy) will draw participants' blood for viral load assessment at the APLA Health and Wellness clinic. Alternately, participants can go directly to a Quest lab (where Rise blood samples are sent for processing) to have their blood drawn for the study. Viral load suppression will be defined as <200 copies of virus per milliliter of blood plasma.

If participants wish to go to a Quest lab, we will offer ride assistance, specifically, the Circulation program (e.g., to transport clients from APLA Health & Wellness in Koreatown and Long Beach to Quest Diagnostics blood draw sites). For example, APLA Health in Koreatown is at [name], a half mile away from the closest Quest draw site at [name]. Prior to the appointment, APLA project staff will book a ride through the Circulation portal. The client will meet the APLA staff person at APLA Health's location. The Circulation ride will take the staff person and participant to the Quest draw site, and then back to APLA Health, where the remainder of the session will be completed.

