Potential Covariates will be assessed at baseline, and 6-and 12-months post-baseline. We will assess potential covariates that have previously been related to HIV outcomes. Socio-demographics include race/ethnicity, gender, education level, age, income, employment status, housing status, marital/relationship status, sexual orientation, and incarceration history. Spirituality and Religiosity will be assessed with items from HCSUS. We will use the 6-item Social Support Questionnaire, Revised (alpha = .94). To assess Trauma History, participants will indicate lifetime traumatic experiences on a checklist of 9 traumas from the Posttraumatic Stress Diagnostic Scale. We will assess Usual Care by asking participants to complete a checklist of Standard Clinic Practices for Adherence (e.g., pill boxes). To assess Exposure to Other Adherence Programs, we will ask participants whether they received adherence counseling through medical case management (a Ryan White Care Act program) and extent of exposure (number of sessions, information covered). They will complete a checklist of other Social Services Resources accessed at APLA or elsewhere.

We will assess self-reported adherence using items validated against viral load and pill counts: number of doses missed last week; percentage of prescribed medications taken last month (on a visual analogue scale), and ability to take all medications as prescribed in the past 4 weeks.

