### 5A - Procedures - Interventions: Overview

5A1 \* Provide a step-by-step description of this procedure for the studied groups of participants. Include both alterations of their experiences (e.g., novel educational practices, new health services) and administration of any treatments they might not otherwise receive (e.g., medications, nutritional supplements). Note: you will be asked below in 5A2 about assignment of participants to different groups (e.g., different data collection or treatment/control groups). At study enrollment and 6- and 12-months post-enrollment (and post-intervention start), a member of the study team (trained in phlebotomy) will draw participants' blood for viral load assessment at the APLA Health and Wellness clinic. Alternately, participants can go directly to a Quest lab (where Rise blood samples are sent for processing) to have their blood drawn for the study. Viral load suppression will be defined as <200 copies of virus per milliliter of blood plasma.

If participants wish to go to a Quest lab, we will offer ride assistance, specifically, the Circulation program (e.g., to transport

ID: 2016-0940

clients from APLA Health & Wellness in Koreatown and Long Beach to Quest Diagnostics blood draw sites). For example, APLA Health in Koreatown is at [name], a half mile away from the closest Quest draw site at [name]. Prior to the appointment, APLA project staff will book a ride through the Circulation portal. The client will meet the APLA staff person at APLA Health's location. The Circulation ride will take the staff person and participant to the Quest draw site, and then back to APLA Health, where the remainder of the session will be completed.

In the event that participants do not want to get their blood drawn and see APLA Health staff in person due to COVID-19, they will be asked to send photos or screenshots of their most recent HIV viral load lab results to the study team cell phone using WhatsApp, which has end-to-end encryption. Study staff will tell participants to delete the photo from their phone immediately after they send it. APLA staff will transcribe the results from these photos to the medical records data collection spreadsheet (that has ID#s and not participant names), and will securely transmit the data to RAND via Kiteworks. Once the data has been securely transmitted, study staff will delete the photo from the study cell phone.

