**5B3 Biologic Sample or Specimen Testing****5B3.1 \* Will any of the samples or specimens be tested?**

- Yes - during this study
- Yes - but testing will be done later
- No
- Don't know

**5B3.2 \* List the types of testing to be performed (e.g., specific biomarkers or diseases to be tested, generic tests to be conducted) and why.**

We will conduct viral load assessments. Viral load suppression, a main study outcome, will be defined as <200 copies of virus per milliliter of blood plasma.

**5B4 Biologic Sample or Specimen Disposition****5B4.1 \* What will be the ultimate disposition of the sample(s) or specimen(s) collected during this study?**

- A. Destroyed at the end of this study
- B. Anonymous sample(s) banked for future research
- C. Identifiable sample(s) banked for future research

**5E Procedures - Risks****5E1 Breach of Confidentiality Risk****5E1.1 \* In the event a *breach of confidentiality* allowing someone outside of the research team to identify participants in this study, which of the following types of harm might result? (Check all that apply)**

- A. Legal (i.e., criminal or civil liability)
- B. Financial/economic (e.g., damage to employability)
- C. Psychological (e.g., embarrassment, distress)
- D. Social (e.g., damage to reputation)
- E. Other
- F. No anticipated risk

**5E2 Participation Risk****5E2.1 \* Aside from the risks associated with a breach of confidentiality, which of the following types of harm might result from participation in the procedure? (Check all that apply)**

ID: 2016-0940

- A. Financial/economic (e.g., damage to employability)
- B. Physical consequences (e.g., pain, discomfort)
- C. Psychological consequences (e.g., distress, embarrassment, pressure to participate)
- D. Social (e.g., stigma of participation, damage to reputation)
- E. Other
- F. No anticipated risk

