Clinicaltrials.gov Cover Sheet

Official Title: A Randomized Controlled Trial of an Antiretroviral Treatment Adherence Intervention for HIV+ African Americans

NCT03331978

Date: 10.30.2017

Statistical Analysis Plan

Descriptive statistics will be performed on all study variables. If related to the primary study variables, analyses will treat covariates as confounding variables. If we have high retention and find statistically significant differences between respondents and non-respondents at follow-up, we will construct and employ inverse predicted probability nonresponse weights. If item non-response is substantial, we will address it through multiple imputations. We may transform outcomes with skewed distributions (log or other as appropriate) to stabilize error variances and reduce the influence of outliers in regression models.

To assess Rise's effects on adherence and viral load, we will use generalized linear mixed models. Specifically, we will employ a repeated-measures logistic regression approach to predict optimal adherence (i.e., dichotomous adherence) with electronic monitoring data collected at enrollment and each follow-up. We will use as covariates any socio-demographic, psychosocial, and contextual variables that are associated with the adherence outcome. We assume a linear trend over time for adherence. We can also explore non-linear time trends for sensitivity analysis to this specification or assumption. To assess Rise's effects on viral suppression, we will conduct similar logistic regressions predicting viral load (dichotomized as undetectable vs. detectable) at 6- and 12-months post-enrollment. We will use similar repeated-measures linear models to examine Rise's effects on linear adherence (percentage of prescribed doses taken).

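### The viral suppression models do not name the suppression stratum used at randomisation; adding it costs nothing and may recover some power

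*SAP*

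**What the plan says.** **Randomisation.** Protocol 5A2.4 (Intervention) sets "A blocked 1:1 randomization design with stratification by viral suppression". Section 5D1 (Medical Records Assessment) gives the source: "we will obtain permission to extract the two most recent viral loads from medical records, for use in stratification by viral suppression". The stratum is therefore known before allocation.

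**Enrollment viral load.** The study also draws its own sample: "At study enrollment and 6- and 12-months post-enrollment (and post-intervention start), a member of the study team" takes blood for viral load (5A1, Viral Load Assessment).

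**Viral suppression analysis.** The SAP's second paragraph plans logistic regressions, similar to those for adherence, "predicting viral load (dichotomized as undetectable vs. detectable) at 6- and 12-months post-enrollment". It names neither the stratum nor the enrollment viral load. Enrollment data are mentioned only for the adherence model, so baseline suppression does not enter as an outcome row either. Protocol 5B3.2 describes the endpoint as "Viral load suppression, a main study outcome".

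**Covariates.** The rule in the SAP's second paragraph is "We will use as covariates any socio-demographic, psychosocial, and contextual variables that are associated with the adherence outcome". A sentence in its first paragraph says, without a list, that covariates found to be related to the main study variables will be treated as confounders. Neither says when a covariate must have been measured. Protocol 5C5.2 (Surveys) states: "Potential Covariates will be assessed at baseline, and 6-and 12-months post-baseline".

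**The concern.** Stratified randomisation balances the arms on baseline suppression. If the model then ignores the stratum, its standard error still includes outcome variation between strata that the design has already removed from the treatment comparison. The standard error is too large, the test rejects less often than its nominal level, and power is lost. The stakes are precision on a main outcome; validity is not threatened.

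The only route by which baseline suppression could enter the model is a data-dependent one. A stratification factor should be fixed in advance.

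The second, smaller matter is timing. Two of the three occasions on which potential covariates are surveyed follow randomisation. Some of the items are things that Rise tries to change. Adjusting for a follow-up value that Rise had moved could remove part of the Rise effect.

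**Working it through.** **Inputs from the documents.** 350 participants, 175 per group (1A1.2); stratification by viral suppression (5A2.4). The documents give no suppression rates, effect size, alpha or correlation for this endpoint, so there is no power figure of the plan's own to reproduce.

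**Assumptions.** 60% versus 73% suppressed; 60% suppressed at baseline; two-sided 5% test; correlation φ between stratum and follow-up suppression of 0.2, 0.3 or 0.5.

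**Step 1: one time point, no other covariates (large-sample approximation).**
- Model standard error without the stratum: √[(0.60×0.40 + 0.73×0.27)/175] = √(0.4371/175) = 0.0500.
- z = 0.13/0.0500 = 2.60.
- Under stratified allocation the actual standard error is smaller by the factor k = √(1−φ²).
- Null rejection without the stratum: 2Φ(−1.96/k).
- Power without the stratum: Φ((z−1.96)/k).
- Power with the stratum: Φ(z/k−1.96).

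| φ | k | Null rejection without | Power without | Power with | Gain (points) |
|---|---|---|---|---|---|
| 0.2 | 0.980 | 4.5% | 74.4% | 75.6% | 1.3 |
| 0.3 | 0.954 | 4.0% | 74.9% | 77.8% | 2.9 |
| 0.5 | 0.866 | 2.4% | 77.0% | 85.2% | 8.1 |

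Simulation of the logistic model (40,000 trials per setting) agrees. Power is 73.5/74.7/76.1% without the stratum and 74.8/77.6/83.9% with it. Null rejection is 4.4/4.0/2.4% without and 5.0/5.1/5.0% with. With 140 per arm (an assumed 20% loss), power is 64.2/64.6/65.5% without and 65.6/67.8/75.2% with.

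**Step 2: both follow-up times.** This uses a random-intercept logistic model with an assumed correlation of 0.6 between 6 and 12 months, 175 per arm and 4,000 trials per setting. Power is 81.6/81.9/85.1% without the stratum and 83.7/85.1/92.8% with it, a gain of about 2/3/8 points. Null rejection is 4.0/4.0/1.8% without and 4.9/5.2/4.7% with.

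**Step 3: a fairer comparator.** The SAP expects to adjust for something. Suppose the model already holds one prognostic baseline covariate with an assumed latent correlation of 0.45. At a single time point the gain from adding the stratum falls to about 0/1/5 points. Null rejection without the stratum is then about 4 to 5% at the two weaker settings and about 3 to 3.5% at the strongest.

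**Step 4: different assumptions.** Take half of participants in each stratum, a within-stratum odds ratio of 2, and control suppression by stratum of 50/70%, 40/80% or 30/90%. The implied correlation is (difference between strata × 0.5)/√(0.6×0.4), that is 0.20, 0.41 and 0.61. At 12 months, null rejection is 4.3/3.5/1.2% without the stratum and 5.0 to 5.2% with it. Power is 82.7/75.2/54.1% without and 83.8/80.5/70.4% with. The direction is the same, and the loss becomes large only when baseline status is very strongly prognostic.

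**Step 5: timing of covariates.** The covariate list in 5C5.2 includes items that Rise may act on:
- services used ("They will complete a checklist of other Social Services Resources accessed at APLA or elsewhere"), while Rise helps link clients to services (1A1.2);
- social support, which Session 1 sets out to strengthen (5A1, Intervention);
- housing status, for which Rise counselors make referrals (5A1, Intervention).

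The documents give nothing from which to size the effect of adjusting for these, so none is claimed.

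**The case against.** **The SAP does not analyse without covariates.** This stands. Step 3 is nearer to the plan than Step 1, so 1/3/8 points is on the high side, and at the two weaker settings the loss almost disappears.

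**Baseline suppression is not excluded.** This also stands in part. The survey list in 5C5.2 covers questionnaire measures, and viral load is a separate procedure, so its absence from that list shows little. The SAP's general covariate sentence could admit it, most plausibly when it is strongly prognostic and matters most. The fair complaint is that the term is not pre-specified.

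**The covariate rule concerns adherence.** True. It reaches the viral models only because they are called similar. That ambiguity is itself a reason to write the viral models out. No gain is shown for the adherence models.

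**Post-randomisation adjustment is hypothetical.** A reader might infer that the SAP plans to adjust for follow-up values or for mediators. The documents do not support that. The SAP calls covariates confounders, which a value changed by Rise is not, and 5C5.2 lists mediators separately. Adjustment of this kind is permitted but not required, so the gap is one of wording.

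**Conclusion.** The omission is certain; its size is not. The stratum used at randomisation is not a named term in the viral suppression models. On the assumed rates at one time point with 175 per arm, naming it is worth about 1/3/8 points of power against a model with no covariates, and about 0/1/5 points against a model with one prognostic baseline covariate. Every rate and correlation behind these figures is an assumption.

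A reader might infer that ignoring the stratum invalidates the test or produces false positives. It does not. In the no-covariate settings null rejection without the stratum stayed below 5%, and with one covariate it stayed at about 5% or lower. A reader might also infer a large loss of power. That would need baseline suppression to be strongly prognostic and nothing correlated with it to be in the model, and the documents establish neither.

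This should be fixed because the remedy is free. The timing of covariates is a secondary clarification.

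**What to change.** 1. Write out the viral suppression model and include the viral-suppression stratum, as used at randomisation, as a fixed term. State that the resulting odds ratio is a within-stratum one.
2. Optionally add the enrollment viral load where it was drawn before randomisation or before any Rise session. In the random-intercept model it adds a further 0/1/3 points if it predicts no better than the stratum, and 2/3/5 points if its correlation with follow-up is 0.1 higher. It needs a missing-data rule, because venipuncture may be declined (5F2.3, Surveys). The order of draw and randomisation is not stated (7A1 and 7A6 comments) and should be recorded.
3. Limit efficacy-model covariates to a fixed list of values measured before randomisation, such as the first-visit survey (7A1 comment). The 6- and 12-month survey values remain available as secondary outcomes, as mediators for Aim 2, and to describe usual care.
4. Date the change and make it before outcomes are analysed by arm. This matters because the anticipated end of data acquisition was 10/31/2021 (3A2.1) and the protocol export is dated November 2022.

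The cost is SAP wording. The stratum already exists, so no participants, visits or tests are added.

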Compared to Whites, Black people living with HIV are less likely to adhere to antiretroviral treatment (ART) and be virally suppressed. Our research has identified culturally relevant factors contributing to disparities among HIV-positive Black Americans, including stigma and medical mistrust (e.g., "conspiracy beliefs," that ART is poison), in addition to structural and psychosocial factors related to poverty, healthcare access, and mental health. However, ART adherence interventions have rarely been culturally congruent, which may explain why relatively few interventions have shown robust effects on adherence or viral suppression. We propose to conduct a randomized controlled trial (RCT) of Rise, a culturally congruent adherence counseling intervention for HIV-positive Black men and women. Rise counselors possess specialized HIV treatment knowledge and are trained in motivational interviewing (MI) skills to overcome culturally relevant barriers to adherence and retention in care; they also assist with linkage to social services. Rise is ideally implemented in community organizations, enabling clients to seek services in non-medical settings, which helps to overcome mistrust of healthcare, and increase readiness for adherence. In a pilot RCT, Rise led to increased adherence (measured by electronic monitoring) relative to a wait-list control group over time, showing a large effect size (Cohen's  $d=.87$ ). However, the pilot did not evaluate effects on viral suppression or include long-term follow-up. Thus, we propose to conduct an RCT of Rise that follows best practices for evidence-based HIV treatment adherence intervention design and testing. The Specific Aims are: (1) To conduct a randomized controlled trial to examine the effects of a culturally congruent adherence intervention on antiretroviral treatment adherence, retention in care, and viral suppression among Black men and women living with HIV; (2) To examine culturally relevant mediators (e.g., medical mistrust, stigma) that may help to explain the effects of the intervention on antiretroviral treatment adherence, retention in care, and viral suppression among Black men and women living with HIV; and (3) To conduct a cost effectiveness analysis of the intervention. A total of 350 Black men and women will be randomly assigned to the intervention or usual care control group (175 per group). Adherence will be electronically monitored daily (and downloaded bi-monthly) from 1-month pre-enrollment to 12-months post-baseline. Viral load will be assessed through venipuncture at baseline and 6- and 12-months post-baseline. If Rise is found to be effective, the next step would be to conduct research to determine effective and feasible methods for intervention implementation and dissemination to community settings.

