**3C1.5** **\* If "N" above, please describe the interaction procedure.**  
 Adherence will be measured continuously and electronically from 1 month prior to the baseline survey to 12-month follow-up using MEMS. One and a half months prior to the baseline session (to decrease reactance to the adherence measurement for a valid baseline measure), interviewers will assist clients with dispensing the medication with the most complex dosing schedule or the base medication of the regimen if all medications have the same schedule (e.g., non-nucleoside reverse transcriptase inhibitor, protease inhibitor, integrase inhibitor), into a MEMS bottle. Bi-monthly, starting at baseline, interviewers will download adherence data and participants will complete a brief survey to assess instances in which the cap was not used as intended in the past two weeks (i.e., how often the bottle was opened without removing a dose, a dose was taken from a source other than the bottle, such as a pillbox, and whether multiple doses were removed at a time and pocketed for later ingestion). Data for the past two weeks at each time-point will be adjusted using these responses for a more valid assessment. MEMS software can calculate the percentage of total scheduled doses actually taken, which will be dichotomized at  $\geq 85\%$  of doses taken at each time-point, following research suggesting that moderate adherence can have clinically significant effects.

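### The SAP splits viral load into undetectable and detectable with no number, but the protocol defines suppression, a main outcome, as <200 copies/mL

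*SAP*

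**What the plan says.** The second paragraph of the SAP covers the two main outcomes. The viral load sentence begins "To assess Rise's effects on viral suppression" and continues: "we will conduct similar logistic regressions predicting viral load (dichotomized as undetectable vs. detectable) at 6- and 12-months post-enrollment". The SAP gives no threshold and no detection limit, and it does not refer to the protocol for either.

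The protocol gives a number. Section 5B3.2 (Viral Load Assessment) states: "Viral load suppression, a main study outcome, will be defined as <200 copies of virus per milliliter of blood plasma". Section 5A1 of the same procedure and section 5D1 (Medical Records Assessment) state: "Viral load suppression will be defined as <200 copies of virus per milliliter of blood plasma". The sentence occurs four times in three form fields, because 5D1 contains it twice.

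Suppression matters elsewhere in the design. Aim 1 (section 1A1.2) concerns effects on "antiretroviral treatment adherence, retention in care, and viral suppression among Black men and women living with HIV", and section 5A2.4 stratifies randomization by viral suppression.

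**The concern.** The SAP names the protocol's outcome and then describes a coding that is not the protocol's. An analyst working from the SAP alone could not recover the 200 copies/mL cut, and one who followed its words could apply a different one. If the words are followed literally, the model estimates the effect of Rise on a stricter outcome than the one the protocol defines.

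Two features of this trial add to the problem. First, viral loads do not all come from one source. Most come from study draws processed at Quest, but under the COVID-19 procedures in sections 5D1 and 5A1 participants may send a photo of their own latest laboratory result. Whether a result is called undetectable could then depend on the reporting laboratory. A fixed cut of 200 would not have that weakness, provided each assay can measure below 200. Second, while both readings remain open, the coding of low but measurable values could be settled after results have been seen.

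**Working it through.** This is mainly a comparison of texts; the only arithmetic is a statement of scale.

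**1. Is there a text that links the two definitions?**

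| Place | Wording in substance | Number given |
|---|---|---|
| SAP, second paragraph | undetectable / detectable | none |
| Protocol 5D1, 5A1 (Viral Load Assessment), 5B3.2 | suppression | <200 copies/mL |
| Protocol 4A2.1, criterion 4b | detectable viral load, for eligibility | none |
| Protocol 4A5.6, flier slogan | being undetectable | none |

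No passage equates undetectable with <200, and no assay limit is stated anywhere. The cut of 200 is the only numeric viral load threshold in either document.

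**2. Is a missing number in the SAP enough to raise this?** No. The SAP also leaves out the adherence cut; it says only that the model will "predict optimal adherence (i.e., dichotomous adherence) with electronic monitoring data". The protocol supplies that cut in 3C1.5: "MEMS software can calculate the percentage of total scheduled doses actually taken, which will be dichotomized at" 85% or more (repeated in 5C2 for MEMS). The adherence wording names no categories of its own, so it is compatible with 85%. The viral load wording does name its own categories, and they are not tied to 200.

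**3. Where do the two codings disagree?** Let *V* be the result and *L* the assay limit, with *L* < 200 (assumed).

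| Result | Protocol | SAP read literally |
|---|---|---|
| *V* < *L* | suppressed | undetectable (success) |
| *L* ≤ *V* < 200 | suppressed | detectable (failure) |
| *V* ≥ 200 | not suppressed | detectable (failure) |

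Only the middle row differs, and every recode there goes from suppressed to failure.

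**4. Scale.** The planned sample is 350, or 175 per group (section 1A1.2). If a share *s* of participants falls in the middle row at a visit:

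number recoded = 350 × *s*; for *s* = 1%, 350 × 0.01 = 3.5 participants.

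The documents do not give *s*. For assumed values of 2%, 5%, 10% and 15%, the formula gives 7, 17.5, 35 and 52.5. With *s* = 0 the codings coincide. The formula also assumes that all 350 have a result at the visit, so missing results would reduce the counts.

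**5. Effect on the comparison.** Write the suppressed proportions under the protocol as *p*₁ and *p*₀, and the shares in the band as *s*₁ and *s*₀. Under the literal coding the difference between arms becomes

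(*p*₁ − *s*₁) − (*p*₀ − *s*₀) = (*p*₁ − *p*₀) − (*s*₁ − *s*₀).

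It is unchanged only if the band holds the same share in both arms. The documents give none of these four quantities, so neither the direction nor the size of a change in the estimated effect can be stated. They also give no significance level, power or target difference for viral suppression, so no power figure is offered.

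**The case against.** The strongest reply is that the definition is already supplied. The SAP sentence opens with viral suppression, which is the protocol's term; the protocol gives that term one operational meaning, and 200 is the only viral load number in either document. The SAP is two paragraphs long and leaves the adherence cut to the protocol too. The study team also uses detectable and undetectable without a number in eligibility criterion 4b and in a flier slogan, which makes loose shorthand more plausible than a deliberately different endpoint. Finally, harm requires a literal reading, an assay limit below 200 and some results in the band, and none of these is established.

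Much of this stands. Shorthand is a reasonable reading, no intent to use another cut is alleged, and the consequence cannot be sized. It does not remove the mismatch. An unnumbered eligibility term and a slogan do not define an outcome, and no text tells the analyst to read undetectable as <200. The SAP states a coding rule that, followed as written, can count protocol-suppressed results as failures. The two documents differ in date (the SAP is dated 10.30.2017; the protocol record was last updated in April 2022), but neither text is an amendment log, so the mismatch is between current texts.

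**Conclusion.** The difference in wording is certain: the SAP's categories for a main outcome do not match the protocol's definition, and nothing reconciles them. Whether a different outcome would actually be modelled is open, because the SAP phrase may be shorthand.

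If it is taken literally, the outcome is stricter than the protocol's. The scale is 3.5 participants recoded per visit for each 1% of 350 in the band, all towards failure. That rests on an assay limit below 200, which the documents do not state, and on a band share that they do not give and that could be zero. The point should be fixed before analysis: the ambiguity concerns the coding of a main outcome, and removing it costs almost nothing.

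**What to change.** In the SAP, replace the undetectable/detectable wording with viral suppression coded as <200 versus ≥200 copies/mL at 6 and 12 months, and cite the protocol definition. If an analysis at an assay limit is also wanted (none is planned now), label it as a sensitivity analysis and give one numeric limit that applies to all sources of results. The cost is one phrase in the SAP, with no new data and no change to study procedures.
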